4.5.8 TIME TO HAZE

Time to haze and number of blinks to clear while wearing study CLs will be measured at V2 and V3, using a computerized chart capable of displaying letters at varying contrast levels at a distance of 1m. Participants will be seated in front of the chart and 5 letters of a given acuity size (6/19) will be displayed. Participants will be asked to read the letters while the contrast of the letters will be reduced until the participant cannot read all 5 letters anymore. The contrast will be adjusted back to the last level where participants can still read all 5 letters. The following measurements will be taken:

- *Time to haze (seconds): After 3 consecutive blinks, the participant is asked to keep their eyes open while continuously looking at the row of letters. The time until at least one letter is no longer “legible” is measured using a stopwatch.*

- *Blinks to clear (integer count): Starting immediately after first observation of haze, the participant is given verbal instructions at 1s intervals to blink until all 5 letters are clear again. The number of blinks it takes for the subject to clear the letters is counted.*

5 MONITORING PROTOCOL ADHERENCE

All personnel involved in this study will be listed on a delegation log and their training will be documented. Consent documentation will be reviewed by personnel not involved in the consent process. Visit windows will be reviewed when determining the analysis cohort. All adverse events and protocol deviations will be reviewed by the Lead Investigator. Serious adverse events and major protocol deviations will be reviewed by the Principal Investigator.

6 POTENTIAL RISKS AND BENEFITS TO HUMAN PARTICIPANTS

This is a minimal risk study because of the use of marketed products and standard optometric assessments.

Contact lenses in this study will be worn on a daily wear (and daily disposable) basis. Adverse events and/ or complications in daily wear of soft contact lenses can occur (e.g. inflammation and infection). Complications that may occur during the wearing of contact lenses include discomfort, dryness, aching or itching eyes, excessive tearing, discharge, hyperemia and variable or blurred vision. More serious risks may include photophobia, iritis, corneal edema or eye infection. Although contact lens-related infections are very infrequent, the possibility does exist. The incidence of infection due to daily-wear soft lenses is 0.035%. Almost always an infection will occur only in one eye. Thirty five million Americans who currently wear contact lenses assume this risk.

When contact lenses are worn on a daily wear basis there is a small risk of an adverse event compared to not wearing contact lenses. When contact lenses are worn on an extended wear basis, there is a significantly increased risk of an adverse reaction compared with wearing contact lenses on a daily wear basis.

A dye (fluorescein) normally used for eye exams is being used in this study. Although rare, it is possible that participants may have an allergic reaction to the dye. This could cause discomfort to their eye.

Participants are advised to inform the investigator of any sensitivities to any ophthalmic drops or study products.

Additionally, it is possible that participants may experience temporary discomfort associated with the study procedures /products including: burning and stinging, blurred vision, sandiness or grittiness, light sensitivity, dryness, itching, crusty eyes and foreign body sensation.

Participants may not benefit directly from taking part in this study. Participants will have the opportunity to try a different type of soft contact lenses at no cost to them, to see whether it provides them with improved symptoms during digital device use.

Information from this study may help researchers come up with new soft contact lens designs to help others in the future. This study may help the study sponsor to better understand the performance of the products being used in this study, particularly during digital device use.

7 ADVERSE EVENTS

See CORE SOP012_v02 for a description of all adverse events, including management and reporting.

Any observations taking place prior to determining that a subject meets all inclusion/ exclusion criteria for the study and which are not related to the performed study procedures are not considered an AE. An AE can be any unfavourable and unintended sign, symptom, or disease temporarily associated with a study procedure, whether there is a causal relationship or not.

8 DISCONTINUATION FROM THE STUDY

Participants may be discontinued at the discretion of the investigator or sponsor in consideration of participant safety or protocol compliance, or at discretion of the participant. Participants discontinued from a study will be reimbursed \$20 per hour for their active involvement in the study (including the initial screening visit). Upon discontinuing, a participant will be offered the option of their data being withdrawn from future statistical analysis. The following is a list of possible reasons for discontinuation from the study:

- Screening failure: Participants will be discontinued if they do not meet the inclusion and exclusion criteria outlined in section 4.2.2.
- Unacceptable performance with products to be used in study: Participants may be discontinued if they are unable to achieve acceptable comfort and /or vision with the study products.

- Positive slit lamp finding: Participants may be permanently discontinued from the study depending on the severity of the condition and on the judgement of the investigator.
- Adverse event: If a participant experiences an adverse event during the study they may be discontinued based on the clinical judgement of the investigator.
- Symptoms: If the participant has persistent symptoms they may be discontinued based on the clinical judgement of the investigator.
- Disinterest, relocation or illness: The participant may choose to discontinue due to reasons within or beyond their control.
- Violation of protocol or non-compliance: The participant will be discontinued if they are unable or unwilling to follow the protocol specified visit schedules and/or study procedures.
- Instillation of topical ocular medication: The participant will be discontinued if they elect to use a topical ocular medication during the study unless that topical ocular medication is prescribed for a limited duration (less than two weeks) to treat a transient condition; in this case the participant may remain an active participant (at the discretion of the investigator) after stopping topical ocular medication following resolution of the ocular condition).
- Lost to follow-up: The participant will be discontinued if they cannot be contacted and do not return for a final exit visit, and if the investigator has made a reasonable effort to contact the participant for a final study visit.
- Premature termination of the study by the sponsor, CORE or the Office of Research Ethics at the University of Waterloo.

A discontinuation form , stating the reason for discontinuation will be completed, which requires the signatures of both the participant and the investigator except where the participant is lost to follow-up in which case only the signature of the investigator is required.

All discontinuations including their reasons will be included in the final report.

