4.4.4 DAY 14 FOLLOW-UP & EXIT (VISIT 3)

Participant to attend visit after 6 hours or more of Precision1 study lens wear.

1. Collect unused study CLs;
2. Changes in medical history/medications;
3. Compliance with # of CL wear days/hours per day (total & comfortable) and # hours of digital device use over past 2 weeks and for V3 visit day;
4. Collect and review at-home ratings;
5. Study CL logMAR HIHC VA for OD, OS and OU;
6. Subjective ratings (0-100 scale, where 100 means better performance; integer steps, both eyes rated together), to assess a typical day in the past 2 weeks for insertion, after 6 hours of digital device use, and just before CL removal.
 - *Comfort*
 - *Dryness*
 - *Clarity of vision*
7. Satisfaction (4-point Likert scale: strongly disagree, slightly disagree, slightly agree, strongly agree) with Precision1 CLs overall and when using digital devices on a typical day in the past 2 weeks
8. Lens fit & surface assessment
9. Time to haze
10. Lens removal
11. Biomicroscopy examination

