4.4.5 STUDY EXIT

The study exit form will be completed when a participant exits the study. This form will be completed either at study completion, or if the participant is discontinued from the study at another time. A study exit form must be completed for all participants who have taken a study ID number. If in the opinion of the investigator post-study follow-up visits are required, the exit form will be completed after the last follow-up visit.

Exit monocular and binocular distance (HIHC VA logMAR) will be recorded with either the participant's spectacles, refraction or habitual contact lenses. An exit biomicroscopy assessment will be conducted if not already completed on the same day for a concurrent study visit.

After the exit assessments have been completed, the participant and investigator will complete the study completion and remuneration forms. At this time the participant will be considered as having exited the study.

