4.5 STUDY PROCEDURES

Table 3 summarizes the procedures at each visit. The order of procedures is described in sections 4.4.2 to 4.4.4.

Table 3: Summary of procedures to be conducted at scheduled visits

Procedure	Visit 1	Visit 2	Visit 3
	Screening	Baseline & Dispense	Day 14 Follow-up
Informed consent	X		
Participant demographics (age, sex)	X		
Medical history and medications	X		
Changes in medical history/ medications			X
Contact lens history	X		
Digital device use history	X		
HIHC VA (logMAR) (unaided or with habitual spectacles)	X		
Biomicroscopy	X		X
Auto refraction/auto keratometry: horizontal and vertical K readings	X		
Subjective refraction	X		
HIHC VA (logMAR) (study CL)	X		X

Study lens fitting	X		
Eligibility	X		
Subjective ratings (Post-insertion re Comfort, Dryness & Vision)		X	
Lens performance (fit, wettability, pre-lens TBUT, deposition)		X	X
Time to haze		X	X
Study lens dispense		X	
Subjective at-home ratings (Comfort, Dryness & Vision) provided		X	
Review of compliance (CL wear, digital device use, completion of home ratings)			X
Subjective ratings (Comfort, Dryness & Vision)			X
Satisfaction ratings (Likert scale for agreement)			X
Collection of unused study lenses			X
Study Exit			X

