4.5.2 SUBJECTIVE RATINGS

Subjective ratings:

At visit 2, participants will be provided with subjective rating 0-100 questionnaires to assess their first impression with the study CLs post insertion regarding comfort, dryness and clarity of vision.

At the end of visit 2, they will be provided with at-home questionnaires to subjectively rate the experience with the study lenses regarding comfort, dryness and clarity of vision using a 0-100 scale (integer steps; both eyes together), where 100 means better performance. This questionnaire will be completed at home on Days 1, 7 and 10 after Visit 2 (i.e. Day 0), at three different time-points on each of these days: directly after insertion, after 6 hours of digital device use, and at the end of day just before lens removal. In addition, times of lens insertion, first notice of discomfort, and lens removal will be collected.

The same questionnaire will be provided to the participants during V3 to assess their overall 'typical day' experience during the past 2 weeks.

Satisfaction with study CL:

Satisfaction (4-point Likert scale: strongly disagree, slightly disagree, slightly agree, strongly agree) with Precision1 CLs overall and while using digital devices on a typical day in the past 2 weeks will be assessed for the following questions:

- *The study lenses provide good vision all day long;*
- *The study lenses provide good comfort all day long;*
- *I am satisfied with the comfort the study lenses provide when I use digital devices for ≥ 6 hours;*
- *I am satisfied with the vision the study lenses provide when I use digital devices for ≥ 6 hours;*
- *I don't experience eye strain when I wear the study lenses and use digital devices for ≥ 6 hours.*
- *I don't experience eye fatigue (tired eyes) when I wear the study lenses and use digital devices for ≥ 6 hours.*
- *I don't experience episodes of blurred vision when I wear the study lenses and use digital devices for ≥ 6 hours.*

- Overall, these lenses provide good performance when using digital devices for ≥ 6 hours.

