10 STATISTICAL ANALYSIS AND DATA MANAGEMENT

10.1 STATISTICAL ANALYSIS

All data will be analyzed by CORE at the University of Waterloo. Data analysis will be conducted using Statistica, SPSS, or other appropriate software.

Descriptive statistics will be provided for all primary outcome variables as well as information regarding baseline variables (e.g. age, sex).

Subjective ratings, lens fit assessments and time to haze will be compared between Visit 2 (Precision1 Dispense) and Visit 3 (2-week follow-up) using either Paired t-tests or Wilcoxon matched pairs, or using ANOVA, as applicable; statistical significance will be set at 5%. The appropriate tests will be selected based on tests of normality - non-parametric tests will be used for data not showing a normal distribution. For assessments conducted for each eye separately, the right eye will be used for analysis if there is no difference between eyes.

Binomial testing will be conducted to analyze Likert questionnaires (strongly agree, slightly agree, slightly disagree, strongly disagree) to determine whether participants had a positive or negative experience with the test lens.

Additional analysis may be conducted.

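### The satisfaction questionnaire is scheduled only at Visit 3, so participants who stop early because of the lens would normally be missing from the binomial tests, which may modestly overstate the positive share

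*Combined protocol and SAP*

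**What the plan says.** All references are to the combined protocol and SAP.

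- **Stopping because of the lens.** Section 8 lists possible reasons for discontinuation. One is "Participants may be discontinued if they are unable to achieve acceptable comfort and /or vision with the study products". Persistent symptoms and adverse events are also listed, as are reasons unrelated to the lens, such as relocation.
- **When satisfaction is asked.** Section 4.4.4 (Visit 3) schedules the 4-point satisfaction items, "with Precision1 CLs overall and when using digital devices on a typical day in the past 2 weeks". In Table 3 (Section 4.5) the row "Satisfaction ratings (Likert scale for agreement" is marked under Visit 3 only. Section 4.5.2 lists eight items; the last begins "Overall, these lenses provide good performance when using digital devices".
- **What is done at exit.** Section 4.4.5 says of the exit form: "This form will be completed either at study completion, or if the participant is discontinued from the study at another time". It then states "Exit monocular and binocular distance (HIHC VA logMAR) will be recorded", adds biomicroscopy if not already done that day, and ends with the completion and remuneration forms. It names no questionnaire.
- **Analysis.** Section 10.1 says "Binomial testing will be conducted to analyze Likert questionnaires", to judge whether the experience with the lens was positive or negative. It gives no denominator and no rule for dispensed participants without answers.
- **Related provisions.** Section 8 offers anyone who discontinues the option of withdrawing their data, and requires all discontinuations and reasons to appear in the final report.

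**The concern.** Satisfaction during digital device use is the second objective in Section 2, although the Likert items are listed there among the other outcome variables rather than the primary ones. Someone who gives up the lens within two weeks because of discomfort or poor vision is among the people most likely to answer negatively, and is also the person the visit schedule does not ask. There is no control arm in which a similar loss could offset this. If such leavers would not have answered positively, the error runs one way: a positive share among completers is never lower than the same number of positives divided by everyone concerned.

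The timing matters because answers to individual items that are not requested when a participant leaves would be lost. The reason for stopping is recorded, but it does not say how the person would have answered each of the eight items.

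**Working it through.** **Step 1. Is there a route for an early leaver's answers?** The satisfaction items appear at Visit 3 in the visit description, in Table 3 and in Section 4.5.2. The exit section expressly covers earlier discontinuation and lists other assessments. The at-home forms for Days 1, 7 and 10 cover comfort, dryness and clarity of vision, not satisfaction. Three provisions leave room for data from such a person: Section 4.4.1 (data from out-of-window visits are assessed for inclusion), Section 4.4.6 (unscheduled-visit data are entered in the database) and Section 8 (mention of a final exit visit). None of them schedules the questionnaire.

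**Step 2. Inputs from the plan.**
- Up to 35 dispensed and a target of 32 completers (Section 4.2.2), an allowance of 35 − 32 = 3.
- Significance level 5% (Section 10.1).
- The 32 itself reproduces from Section 4.2.1: a two-sided paired t-test with effect size 0.60 has power 0.898 at n = 31 and 0.908 at n = 32, so 32 is the smallest number reaching 0.90. The sample size is not in question.

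**Step 3. Assumptions not in the plan.** L = 1, 2 or 3 dispensed participants stop because of the lens; each counts as not positive; the binomial test is exact, two-sided, against 50%. With L = 0 there is no effect.

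**Step 4. Overstatement of the positive share**, for k positive answers.

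With 32 completers plus L leavers, the formula is k/32 − k/(32+L). With 35 dispensed and 35−L completers, it is k/(35−L) − k/35. Results in percentage points:

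| L | 32 completers, k=23 | 32 completers, k=28 | 35 dispensed, k=23 | 35 dispensed, k=28 |
|---|---|---|---|---|
| 1 | 2.18 | 2.65 | 1.93 | 2.35 |
| 2 | 4.23 | 5.15 | 3.98 | 4.85 |
| 3 | 6.16 | 7.50 | 6.16 | 7.50 |

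Example: 23/32 = 71.9% and 23/35 = 65.7%, a difference of 6.2 points.

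**Step 5. Does the test result change?** Every count k was checked. All changes are listed.

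| Setting | L | Completers only | Leavers added | Change |
|---|---|---|---|---|
| 32 completers | 2 | 23/32, p=0.020 | 23/34, p=0.058 | positive to not significant |
| either setting | 3 | 23/32, p=0.020 | 23/35, p=0.090 | positive to not significant |
| 35 dispensed | 2 | 23/33, p=0.035 | 23/35, p=0.090 | positive to not significant |
| 32 completers | 1 | 10/32, p=0.0501 | 10/33, p=0.035 | not significant to negative |
| 32 completers | 2 | 10/32, p=0.0501 | 10/34, p=0.024 | not significant to negative |
| either setting | 3 | 10/32, p=0.0501 | 10/35, p=0.017 | not significant to negative |
| either setting | 3 | 11/32, p=0.110 | 11/35, p=0.041 | not significant to negative |
| 35 dispensed | 1 | 11/34, p=0.058 | 11/35, p=0.041 | not significant to negative |
| 35 dispensed | 2 | 11/33, p=0.080 | 11/35, p=0.041 | not significant to negative |

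At 24 positives the verdict already holds: 24/32 (p=0.007) becomes 24/35 (p=0.041). With one leaver no positive verdict is lost.

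**The case against.** **The plan may intend early leavers to do the Visit 3 procedures.** Table 2 labels its last row as Visit 3 and exit together, Section 4.4.4 has a similar heading, and Table 3 places study exit in the Visit 3 column. A returning early leaver could therefore be taken through the Visit 3 list as an out-of-window visit. That reading is possible. For this reason the documents do not support the stronger inference that early leavers are excluded by rule. But the headings do not clearly extend the questionnaire to them, and Section 4.4.5, the one section that names their case, does not mention it.

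**The reasons for stopping are recorded and reported anyway.** This stands in part. A reason-based sensitivity analysis would remain possible from the discontinuation forms, so it would be wrong to say that everything is lost. What is lost is the answer to each item.

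**The size is hypothetical.** This also stands. The plan gives no rate of lens-related stopping, three is its whole allowance for non-completion from any cause, and enrolment requires habitual wearers with acceptable fit and acuity in this lens. Those who fail at screening are not dispensed and are outside this point. The study is also a declared pilot.

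**Scoring leavers as not positive is debatable.** A lens-related adverse event does not prove dissatisfaction during device use. Such scoring therefore belongs in a sensitivity analysis, not the main test.

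**A reader might extend the point to the 0-100 ratings.** Section 4.5.2 says "The same questionnaire will be provided to the participants during V3" for the typical-day ratings, so these too are unscheduled for early leavers. But they do not enter the binomial tests. The mean change from Visit 2 to Visit 3 would look too favourable only if leavers' change had been worse than completers', which the documents do not establish: a leaver may already score low at Visit 2.

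**Conclusion.** The concern holds as a minor point about the Likert items. As written, a dispensed participant who stops because of comfort, vision, symptoms or a lens-related adverse event would normally be absent from the binomial tests, and the positive share would be overstated if that person would not have answered positively.

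Under the stated assumptions the overstatement is about 2 to 7.5 percentage points at 23 to 28 positives. A positive verdict is lost only at 23 positives, and only with 2 or 3 leavers; a few results at 10 or 11 positives move from not significant to negative. The number of leavers, their scoring as not positive, the 50% null and the two-sided exact test are all assumptions.

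Two stronger readings are not supported: that the plan excludes early leavers by rule, and that the primary ratings are biased.

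**What to change.** **Section 4.4.5.** State that anyone who stops after dispensing and attends an exit visit completes the satisfaction questionnaire, worded for the period the lenses were actually worn, and returns any completed at-home ratings. The rewording is needed because the current items refer to a typical day in the past two weeks, which does not suit someone who stopped after a day or two.

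**Section 10.1.** Include these exit answers in the binomial tests. For each item, show the number dispensed and the number answering. Add a sensitivity analysis that counts lens-related discontinuations without answers as not positive on the overall-performance item, the last in Section 4.5.2. Leave out participants who withdraw their data, but report their number and reasons.

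**Cost.** One short questionnaire at early exit and a few lines of analysis text. The reported satisfaction percentage may be lower. Leavers who do not return, or who withdraw their data, will still be missing from the main tests; the displayed denominators make that visible.

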9 STUDY COMPLETION AND REMUNERATION

At the last scheduled protocol visit a study completion form will be completed, which requires the signatures of both the participant and the investigator.

Once their involvement in the study is complete, participants will be informed about receiving feedback following study completion in the Letter of Appreciation.

Participant remuneration will be \$60 for completing the study this includes \$50 for active time and \$10 for completing the at-home questionnaires.

